**MVPA on each day of the study (Baseline to final treatment day 21)**

The variable used is the total number of minutes of MVPA calculated for each study day.

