## 1. Document History

Document Version	Date	Reason for changes
1.0	29OCT2024	Final version
2.0	05DEC2024	
Updates from the DRM:
 

• Section 7.1: Date of Last Study Treatment Administration updated include data collected in the End of Study Termination CRF

• Section 7.1: Study day definition updated to:

◦ Study Day = Date of assessment/event – Date of Baseline Visit.

• Section 7.1 Baseline derivation updated in line with new study day definition.

• Section 7.4.7 updated to exclude day 21 in the analysis due to Day 21 being a partial day.

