## **7.4.7 Efficacy Variables**

### **7.4.7.1 Primary Efficacy Variable**

For primary analysis, average minutes of MVPA on Day 7 will be calculated over all non-missing days between study day 1 (product usage) through 7, inclusive and it is collected via the Actigraph device. Average minutes of MVPA on Day 14 will be calculated over all non-missing days between study day 8 through 14, inclusive. Average minutes of MVPA on Day 21 will be calculated over all non-missing days between study day 15 through 20, inclusive. Any days beyond day 20 will be excluded from all summaries and analyses and will only be present in listed data.

Average baseline MVPA is computed as:

- Average baseline MVPA = total minutes of MVPA over the baseline period / number of days with non-missing data over the baseline period.
  - Baseline period is defined in section 7.1.

Average MVPA for each 7-day period is calculated as:

- Average MVPA for 7-day period = total minutes of MVPA over the period / number of days with non missing data over the period.
  - If every day within the 7 – day period has non missing data, then the Average MVPA for 7- day period will be computed as: total minutes of MVPA over the period / 7.

Change from baseline is calculated as:

- Average MVPA for 7-day period - Average baseline MVPA.

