### **7.4.7.2 Secondary Efficacy Variables**

#### **Change from baseline on Days 7, 14, and 21 in Daily Average number of steps taken**

Average baseline number of steps taken is calculated as:

- Average baseline number of steps taken = total number of steps taken over the baseline period / number of days with non missing data over the baseline period.
  - Baseline period is defined in section 7.1.

Daily average number of steps taken for each 7-day period is calculated as:

- Daily average number of steps taken for 7-day period = total number of steps over the period / number of days with non missing data over the period.

Change from baseline is calculated as:

- Daily average number of steps taken for 7-day period - Average baseline number of steps taken.

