#### 10.6.2 Secondary Efficacy Analysis

Change from baseline at day 7, day 14 and day 21 tables are summarized by summary statistics by timepoint along with the analysis results specified in section 8.2.3 for the mITT, for each of the following secondary endpoints:

- Daily Average number of steps taken in Table **CCI**
- Ratio of sedentary/non-sedentary time in Table **CCI**
- Gait, assessed through speed and step irregularity in Table **CCI**
- Indices of morning stiffness in Table **CCI**
- WOMAC scores including Pain, Stiffness and Physical function subscales in Table **CCI**
- NRS in in Table **CCI**

Change from baseline at day 7, day 14 and day 21 tables are summarized by summary statistics by timepoint for the mITT, for each of the following secondary endpoints:

- MVPA on each day of the study in Table **CCI**
- Karolinska Sleepiness Scale in Table **CCI**
- EQ-5D-5L Index in Table **CCI**

Table **CCI** summarizes EQ-5D-5L response data over time by treatment and overall.

Listings CCI [REDACTED] present all data for each of the endpoints for the mITT.

Figures CCI [REDACTED] presents over time graphs for each of the endpoints for the mITT.

Figure CCI [REDACTED] presents the correlation between WOMAC scores and MVPA for the mITT.

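### SAP v2.0's exclusion of the partial Day 21 was not carried through: daily MVPA still runs to Day 21, and the third window of the other tracker endpoints has no day numbers

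*SAP*

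**What the plan says.** The SAP change log (Section 1, Document History) records for v2.0: "Section 7.4.7 updated to exclude day 21 in the analysis due to Day 21 being a partial day". Section 7.4.7 holds all efficacy variables: primary (7.4.7.1), secondary (7.4.7.2) and exploratory (7.4.7.3). The schedule in SAP 3.3 has the device returned on Day 21 (Visit 3).

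Section 7.4.7.1 carries out the change for the primary variable: "Average minutes of MVPA on Day 21 will be calculated over all non-missing days between study day 15 through 20, inclusive". It then adds: "Any days beyond day 20 will be excluded from all summaries and analyses and will only be present in listed data". Protocol 13.3.1 used Days 15-21 for this window and excluded only days after Day 21.

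Elsewhere the text was not changed to match:

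- Section 7.4.7.2 keeps the endpoint "MVPA on each day of the study (Baseline to final treatment day 21" and defines it as the total MVPA minutes of each study day, with no adjustment for wear time.
- Section 8.2.3 gives the same range in its list of endpoints that are described without a formal test.
- Section 10.6.2 lists "MVPA on each day of the study in Table" under the tables of change from baseline at Days 7, 14 and 21.
- Steps in 7.4.7.2 are "total number of steps over the period / number of days with non missing data over the period". The period is called a seven-day period and its days are not numbered. The same holds for the sedentary ratio, cadence, gait speed and post-wake activity.

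Section 8.2 restricts the tracker analyses to subjects with at least 3 valid days (20 hours of wear or more) at baseline and in each later period. Section 3.5, which lists changes from the protocol, mentions only the mITT definition.

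**The concern.** A programmer cannot both keep everything after Day 20 out of all summaries and produce a daily MVPA summary to Day 21. For the other tracker endpoints, the programmer must guess whether the third window ends on Day 20 or Day 21.

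The choice matters because a day cut short by returning the device yields a low daily total for a reason unrelated to the subject's activity. A daily MVPA table or plot that ran to Day 21 would show a drop at the last time point. If the step mean included that day, the third-window change in a formally tested endpoint would be too low, and primary and secondary tracker results would cover different days. The bias would run downward, against showing improvement.

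**Working it through.** **Does any stated rule remove a short Day 21?**

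1. The 20-hour rule in SAP 8.2 decides which subjects are analysed. A subject with three valid days among Days 15-20 qualifies whatever happens on Day 21.
2. The averages in 7.4.7.1 and 7.4.7.2 divide by days with non-missing data. A truncated day is short but not missing, so it would count as one day in the divisor.
3. Daily MVPA is a raw total of minutes.

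Only the Day 20 sentence could remove it, and the scope of that sentence is what is unclear.

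**Window lengths.** Days 15-20 are 20 − 15 + 1 = 6 days. Days 15-21 are 7 days. The primary variable nevertheless uses the label "Average MVPA for 7-day period = total minutes of MVPA over the period / number of days with non missing data over the period" for its six-day third window, so the words seven-day period do not settle the matter either way.

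**Size if Day 21 were used.** Let *f* be the share of a full day's activity recorded on Day 21. The documents give neither *f* nor a visit time, so a range is assumed. Values of 0.25 to 0.75 are taken directly. As a second route, spread activity evenly over 07:00-22:00 (15 hours), so that return at hour *h* gives *f* = (*h* − 7)/15.

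- Shortfall in the Day 21 daily total: 1 − *f*.
- Shortfall in a seven-day mean of daily totals, with six full days and one partial day: 1 − (6 + *f*)/7 = (1 − *f*)/7.

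| Assumption | *f* | Day 21 MVPA low by | Seven-day step mean low by |
|---|---|---|---|
| Return 10:00 | 3/15 = 0.20 | 80% | 0.80/7 = 11.4% |
| Direct | 0.25 | 75% | 0.75/7 = 10.7% |
| Return 12:00 | 5/15 = 0.33 | 67% | 0.67/7 = 9.5% |
| Direct | 0.50 | 50% | 0.50/7 = 7.1% |
| Return 15:00 | 8/15 = 0.53 | 47% | 0.47/7 = 6.7% |
| Direct | 0.75 | 25% | 0.25/7 = 3.6% |

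**Which endpoints does this arithmetic fit?** It fits daily totals only: daily MVPA, and steps if Day 21 is in the window.

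- The sedentary ratio for a period is total minutes over total minutes, so a short day is weighted by its length and the direction of any shift is not fixed. In an invented example, six days have 600 sedentary and 300 non-sedentary minutes each (ratio 2.00). Adding a short day of 300 and 60 minutes gives 3900/1860 = 2.10. Adding one of 240 and 150 gives 3840/1950 = 1.97.
- Cadence and gait speed are averages of daily means, not daily totals.
- Post-wake counts cover only the first 30 or 60 minutes and are complete if the device is returned later than that.

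**A related slip.** Section 7.4.7.1 also gives a divisor of 7 for a period with every day present. Applied to six days' minutes, it would understate the mean by 1 − 6/7 = 14.3%.

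The sample size (147 completers, 195 enrolled) does not enter this point.

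**The case against.** The strongest reply is that the SAP already excludes Day 21. The change log names the whole of 7.4.7, and the cut-off sentence covers every summary and analysis. The Day 21 wording for daily MVPA repeats the protocol's endpoint title, and the primary endpoint also keeps its Day 21 label although its data stop at Day 20. The lead-in in 10.6.2 is one generic sentence shared with the KSS and EQ-5D-5L. The ADaM specification and table shells are separate documents and may fix the window. Daily MVPA is descriptive, and no return time is stated.

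Much of this stands. A reader might infer that v2.0 removed Day 21 from the primary variable alone and plans to use it everywhere else. The documents do not support that: the change log is broader, and the primary variable's own six-day window also carries the seven-day label. Nor do they support the inference that a short day enters every tracker endpoint as if it were full, since only daily totals behave that way.

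A reader might also take the cut-off sentence as deleting the Day 21 questionnaires. The stated reason, a partial day, concerns accumulated tracker data, and 7.4.7.2 and 8.2.3 expressly schedule Day 21 NRS, WOMAC, KSS or EQ-5D-5L results. That is not the intent, but the sentence as worded does not exempt them.

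The reply does not remove the contradiction. The daily MVPA range in 7.4.7.2 and 8.2.3 is more than a label, because it is the only statement of which days are summarised. Section 8.2.3 brings in the analysis method of 8.2.2 for the other endpoints, not the window of 7.4.7.1.

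**Conclusion.** The point holds as an internal contradiction and an undefined window, and the text is wrong as written. The Day 20 cut-off in 7.4.7.1 conflicts with daily MVPA to Day 21 in 7.4.7.2, 8.2.3 and 10.6.2. The third window of the other tracker endpoints is not numbered, and no wear rule drops a short day.

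If Day 21 were used, its MVPA total would be understated by about 25% to 80%, and a seven-day step mean by about 4% to 11%. Both ranges rest on an assumed capture of 75% to 20% of the day's activity. The consequence for daily MVPA is a misleading descriptive summary, with no test affected. For steps, it is a possible downward bias in a tested third-window change. The sedentary ratio, cadence, gait speed and post-wake counts are not biased by this mechanism. The primary window itself is stated as Days 15-20 and is unaffected, apart from the stray divisor of 7.

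**What to change.** - In SAP 7.1, state one rule: for all tracker-derived endpoints the third window is Days 15-20, and daily MVPA is summarised and plotted to Day 20.
- Limit the exclusion sentence in 7.4.7.1 to tracker data, so that the Day 21 NRS, WOMAC, KSS and EQ-5D-5L are kept. Correct the seven-day label and the divisor of 7 for the six-day window.
- Align 7.4.7.2, 8.2.3 and 10.6.2 with the rule.
- State whether days with under 20 hours of wear are dropped from the averages or only counted towards subject inclusion.
- Declare the departure from protocol 13.3.1 (Days 15-21) in SAP 3.5.

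The cost is SAP wording, one window parameter in the ADaM specification, and any matching edits to the table shells. No new data are needed and the sample size does not change.

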**Change from baseline in self-reported pain intensity, assessed through Numeric Rating Scale (NRS) (daily assessment).**

Self-reported pain intensity is recorded on the 'Numeric Rating Scale' eDiary page at each scheduled timepoint.

Baseline is the value collected on Day 0, as described in section 7.1.

Change from baseline is calculated as:

- NRS score at Scheduled Timepoint – NRS baseline score (Day 0)

### **WOMAC Subscale Score (Pain WOMAC A, Stiffness WOMAC B and Function WOMAC C)**

The WOMAC® LK3.0 is composed of 3 subscales (A: Pain, B: Stiffness, C: Physical Function). There are 5 components for subscale A (Pain), 2 components for subscale B (Stiffness), and 17 components for subscale C (Physical Function) each component is measured on a 0-4 scale [1].

A WOMAC subscale score is calculated, at Day 0, Day 1, Day 7, Day 14 and Day 21, as the sum of the available component scores within the subscale. For convenience this is normalized on a 0-100 scale by dividing the sum appropriately:

- Pain WOMAC A = (sum of raw score items in dimension) x 5
- Stiffness WOMAC B= (sum of raw score items in dimension) x 12.5
- Function WOMAC C = (sum of raw score items in dimension) x 1.47

The subscale score will be set to missing according to the following:

- if  $\geq 2$  Pain components are missing
- if both Stiffness components are missing
- if  $\geq 4$  Physical Function components are missing

As outlined in the WOMAC scoring guide [1], if there are missing components within a subscale but the number of missing components does not meet the criteria for setting the subscale score to missing, then the value of the missing components will be set equal to the mean of the available components of the respective subscale.

WOMAC subscale scores and normalized subscale scores are calculated, as described in the previous section, for baseline (Day 0) and for all post baseline timepoints: Day 1, Day 7, Day 14 and Day 21.

Normalized WOMAC subscale scores are used for the following endpoints:

- Change from baseline in WOMAC Physical Function subscale on Days 7, 14, and 21
- Change from baseline in the WOMAC subscales, Pain (composite) and Stiffness (composite) on Days 7, 14, and 21

For each scheduled time point:

- Baseline is the value collected on Day 0, as described in section 7.1.
- Change from baseline is calculated as:
- Normalized WOMAC subscale score at Scheduled Timepoint – Normalized WOMAC subscale baseline score (Day 0)

### **WOMAC Global Score**

The total WOMAC® LK3.0 global score, calculated at, Day 0, Day 1, Day 7, Day 14 and Day 21, is computed as the sum of the 3 normalized WOMAC subscale scores.

The total WOMAC score will be set to missing if any of the WOMAC subscale scores are set to missing as defined above. The WOMAC global score is:

$$\text{WOMAC Global Score} = \text{WOMAC A} + \text{WOMAC B} + \text{WOMAC C}$$

WOMAC Global Score and change from Baseline is calculated at all visits.

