## 3 STUDY OBJECTIVES AND ENDPOINTS

**Table 3-1 Study Objectives and Endpoints**

Objective(s)	Endpoint(s)
Primary	
To evaluate the effects of Voltaren Gel on physical activity, measured through connected activity tracker.	Change from baseline in the average minutes of Moderate and Vigorous Physical Activity (MVPA), at Week 1 (days 1-7), Week 2 (days 8-14), and Week 3 (days 15-21).
Secondary	
To evaluate the effects of Voltaren Gel on functional mobility, measured through connected activity tracker	
Change from baseline on Days 7, 14, and 21 in:
 
 
• Daily Average number of steps taken
 
• Ratio of sedentary/non-sedentary time
 
• Gait, assessed through speed and step irregularity (measured via cadence and gait speed)
 
• Indices of morning stiffness (assessed through levels of activity 30- and 60-mins post-wake)
 
 
Indices of level of stiffness throughout the day as assessed via the WOMAC stiffness subscale Change from baseline in:
 
 
• WOMAC Physical Function subscale on Days 7, 14, and 21
 

To assess the functional mobility, measured through connected activity tracker.	Moderate and Vigorous Physical Activity (MVPA) on each day of the study (Baseline to final treatment day 21).
To evaluate the effects of Voltaren Gel on functional mobility, measured through subject related outcomes	Study subjects' perceived ability to exercise more regularly. Assessed using the WOMAC Physical Function subscale on Days 7, 14, and 21
To evaluate the effects of Voltaren Gel on pain intensity	Change from baseline in self-reported pain intensity, assessed through Numeric Rating Scale (NRS) (daily assessment).
To evaluate the effects of Voltaren Gel on activity-related pain and stiffness	Change from baseline in the WOMAC total score and subscales on Days 7, 14, and 21: 
 
• Pain (composite)
 
• Stiffness (composite)
 

Property of Haleon - Confidential

May not be used, divulged, published or otherwise disclosed without the consent of  
 Haleon

Clinical Protocol Template, TMF-187821, v11.0. Parent SOP: **CCI**

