## 16.2 STUDY QUESTIONNAIRES

### 16.2.1 Western Ontario and McMaster Universities Arthritis Index (WOMAC) 5-point Likert scale example

Severity, on average, during the last 48 hours, of:

Pain	None	Slight	Moderate	Severe	Extreme
Pain – Walking					
Pain – Stair climbing					
Pain – Nocturnal					
Pain – Rest					
Pain – Weightbearing					

Stiffness:

Morning Stiffness					
Stiffness occurring during the day					

Level of difficulty performing the following functions, on average, during the last 48 hours:

	None	Slight	Moderate	Severe	Extreme
Descending stairs					
Ascending stairs					
Rising from sitting					
Standing					
Bending to the floor					
Walking on flat					
Getting in/out of a car					
Going shopping					
Putting on socks					
Rising from bed					
Taking of socks					
Lying in bed					
Getting in/out of bath					
Sitting					
Getting on/off toilet					
Performing heavy domestic duties					
Performing light domestic duties					

The WOMAC parameters are:

0 – none, 1 – slight, 2 – moderate, 3 – severe, 4 – extreme.

The index is out of a total of 96 possible points, with 0 being the best and 96 being the worst

Property of Haleon - Confidential

May not be used, divulged, published or otherwise disclosed without the consent of  
 Haleon

[figure not shown]
Clinical Protocol Template, TMF-187821, v11.0. Parent SOP: **CCI**

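### The SAP's WOMAC Global Score (0 to about 300) is not the 0-96 item sum described in the protocol, and SAP 3.5 does not declare the difference.

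*SAP*

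**What the plan says.** Protocol Table 3-1 includes this secondary endpoint: "Change from baseline in the WOMAC total score and subscales on Days 7, 14, and 21". The table gives no scoring rule, and neither does protocol 13.3.2. The only scoring is in protocol appendix 16.2.1, which lists 5 pain, 2 stiffness and 17 function items, codes them "0 – none, 1 – slight, 2 – moderate, 3 – severe, 4 – extreme", and states: "The index is out of a total of 96 possible points, with 0 being the best and 96 being the worst".

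SAP 7.4.7.2 uses the same instrument and item counts. It rescales each subscale, saying "For convenience this is normalized on a 0-100 scale". The pain rule is "Pain WOMAC A = (sum of raw score items in dimension) x 5"; the stiffness and function factors are 12.5 and 1.47. The total is then "computed as the sum of the 3 normalized WOMAC subscale scores".

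SAP 8.2.3 lists change in this Global Score among the secondary endpoints analysed in the same way as the primary endpoint. SAP 3.5, the section for departures from the protocol, records only a change to the mITT definition.

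**The concern.** Rescaling one subscale by a constant changes its units and nothing else. Adding three subscales that were multiplied by different constants produces a different variable from the plain item sum. Someone who reads the protocol and then the results table would expect a 0-96 score, but would be looking at one that runs to about 300, in which two stiffness questions count for as much of the maximum as seventeen function questions.

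What is at stake is the estimate and test for one secondary endpoint. Under SAP 8.2.2, as applied by SAP 8.2.3, the intercept p-value also decides whether the by-timepoint model is fitted. The choice of total could therefore affect which results appear for this endpoint as well as their size. SAP 8.2.5.3 applies no multiplicity adjustment, so that p-value would be read at face value.

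**Working it through.** **Inputs.** Items: 5 pain (A), 2 stiffness (B), 17 function (C), each scored 0-4 (protocol 16.2.1; SAP 7.4.7.2). SAP multipliers: 5, 12.5 and 1.47.

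**Protocol figure.** Maximum = (5 + 2 + 17) × 4 = 20 + 8 + 68 = 96. This reproduces the stated 96 exactly, so the index is an unweighted item sum: T(protocol) = A + B + C, with A, B and C the raw subscale sums.

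**SAP figure.** T(SAP) = 5A + 12.5B + 1.47C. Maximum = 20 × 5 + 8 × 12.5 + 68 × 1.47 = 100 + 100 + 99.96 = 299.96. The shortfall from 300 arises because 1.47 is 100/68 = 1.4706 rounded, which is immaterial.

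**Share of the maximum score.**

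| Subscale | Protocol | SAP | Per item: protocol → SAP |
|---|---|---|---|
| Pain | 20/96 = 20.8% | 100/299.96 = 33.3% | 4.2% → 6.7% (×1.6) |
| Stiffness | 8/96 = 8.3% | 100/299.96 = 33.3% | 4.2% → 16.7% (×4.0) |
| Function | 68/96 = 70.8% | 99.96/299.96 = 33.3% | 4.2% → 2.0% (×0.47) |

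**Are the totals linear transforms of each other?** That would require equal multipliers, and 5, 12.5 and 1.47 are not equal. Three constructed changes show the consequence:

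- One-level gain on both stiffness items: 2 points on the protocol total (2/96 = 2.1% of range); 2 × 12.5 = 25 points on the SAP total (25/299.96 = 8.3%).
- One-level gain on all 17 function items: 17 points on the protocol total (17/96 = 17.7%); 17 × 1.47 = 24.99 points on the SAP total (8.3%).
- One level better on all 17 function items and one level worse on both stiffness items: 17 − 2 = 15 points better on the protocol total; 24.99 − 25 = −0.01, in effect no change, on the SAP total.

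**Missing items.** SAP 7.4.7.2 sets stiffness to missing only when both items are missing. If one is missing, it takes the value of the other. A single answered item can then determine a component worth 33.3% of the SAP maximum, against 8.3% of the protocol maximum.

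**What is not touched.** Each normalised subscale is a constant multiple of its raw sum, so its own test is unchanged. MVPA and the sample size calculation do not use WOMAC.

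**The case against.** The case for leaving the SAP alone has five parts.

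- The 96-point line is in an appendix headed as an example of the questionnaire. The endpoint table and analysis section give no formula, and protocol 13.3 leaves further analysis detail to the SAP, which states its formula in full.
- Weighting by domain and weighting by item are both explicit composites, and nothing in the documents shows that one is better.
- The total has a small role. Protocol 13.3.2 names the pain and stiffness subscales and not the total, and no confirmatory claim depends on it.
- Pain, stiffness and function are each analysed and tabulated, so a reader can see whether stiffness drives the total.
- The percentages are shares of the maximum score. They do not measure influence on the result.

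Most of this stands, and it limits the point. A reader might infer that stiffness has four times the influence on the change or its p-value, or that the SAP total will look more favourable. The documents do not support that: influence also depends on subscale variances and correlations, which they do not give, and the constructed changes above hold the other items still. A reader might also infer that the SAP tests something wholly outside the protocol's endpoints. That too is more than an example appendix can carry; the endpoint is named, and the SAP operationalises it differently. Nor does either document plan a comparison with another study's 0-96 total or with a threshold on that scale.

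The objection does not remove the mismatch. The appendix line is the protocol's only scoring of the total, the SAP departs from it, and the section meant for such departures is silent. The only reason given for normalising is convenience, and that is said of the subscales.

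**Conclusion.** The point holds as a mismatch in definition that the SAP does not declare. Following the SAP gives a total with a range of 0 to 299.96. Following the only scoring in the protocol gives 0 to 96. The two are not interchangeable: by share of the maximum, stiffness moves from 8.3% to 33.3%, pain from 20.8% to 33.3% and function from 70.8% to 33.3%. The estimate, confidence interval and p-value for the WOMAC total may differ between them, in a direction and by an amount that cannot be worked out from the documents.

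This rests on reading appendix 16.2.1 as the protocol's scoring of its total, which is reasonable because no other rule competes with it. The effect is confined to one secondary endpoint. The point does not depend on preferring one weighting; it is that the documents should describe the same score or say that they do not. It should be corrected, but it does not threaten the trial's main conclusion.

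**What to change.** In SAP 7.4.7.2, derive the total for the protocol's WOMAC total score endpoint as the sum of the three raw subscale scores: 24 items, after the within-subscale imputation already stated, range 0-96. Keep the rule that the total is missing if any subscale is missing, and keep the normalised scores for the subscale endpoints. If a 0-100 presentation is wanted, multiply the 0-96 total by 100/96, which changes the units only.

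If the sum of the normalised subscales is retained, report it as supportive, state its range in the table, and list it in SAP 3.5.

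The cost is one derivation line and a table footnote, plus an entry in SAP 3.5 if the 0-300 sum stays. No new data are needed, because SAP 7.4.7.2 already calculates both raw and normalised subscale scores.
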